## PROTOCOL SYNOPSIS

Title:	Safety and Performance of Metastatic Tumor Cell Trap Device in Patients with Advanced Ovarian Cancer
Protocol Number:	MTRAP-2016-01
Medical Device:	Metastatic Tumor Cell Trap Device (M-Trap)
Intended Use:	M-Trap is an implantable medical device designed to capture disseminated tumor cells (DTCs). It is intended for use in advanced-stage ovarian cancer patients.
Surgical Use:	Up to three (3) M-Trap devices will be surgically implanted via laparotomy in the right and left paracolic (pelvic) gutters and behind segment 6 of the liver within the peritoneal cavity of the patient at the time of surgical resection. Patients will receive standard chemotherapy with carboplatin and paclitaxel. After completion of chemotherapy, M-Trap devices will be removed via minimally invasive surgery (laparoscopy) following the device removal protocol.
Study Design:	Prospective, multi-center, non-blinded, single-arm study. Safety and performance study conducted in accordance with ISO 14155.
Study Objective(s):	The study objective is to assess the safety and the performance of the MTrap device.  Safety objectives: The primary objective is to demonstrate that the safety of M-Trap, as measured by freedom from device- and procedure-related major adverse events through 6-months post-implantation, is non-inferior to historical controls.  The secondary objective is to collect long-term safety data to support device safety and post-market surveillance. Safety will be evaluated to demonstrate acceptable levels of device-related and procedure-related complications.  Performance objective: The primary objective is to confirm M-Trap performance, as determined by histological evidence of tumor cell capture. The secondary objective is to assess disease focalization with use of the M-Trap device.

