## **2. INVESTIGATIONAL DEVICE**

The M-Trap (Metastatic Tumor Cell Trap) device is comprised of a non-resorbable, polycarbonate polyurethane scaffold matrix with a Type I collagen coating. The M-Trap device is provided sterile for single use and is intended to capture metastatic tumor cells in advanced-stage ovarian cancer patients.

The M-Trap scaffold is a biostable, reticulated (possessing interconnected and intercommunicating open pores), polycarbonate polyurethane-urea matrix. The reticulated matrix permits tissue ingrowth and proliferation into the implant. The matrix has a void content greater than 90%, with average cell sizes measuring in the range of 250 to 500 microns. The M-Trap collagen coating is comprised of a [REDACTED] Type I collagen that is [REDACTED] cross-linked for in-vivo durability.

M-Trap devices are manufactured under GMP conditions. Devices are individually packaged in moisture-resistant pouches and sterilized using gamma irradiation. M-Trap is available in an oval configuration of 15 mm (width) x 50 mm (length) x 5 mm (thickness). The device has been demonstrated to be biocompatible and biostable per ISO-10993 testing for a permanent, tissue/bone-contacting implant.

M-Trap is intended to be implanted into the peritoneal cavity during the tumor debulking procedure to capture disseminating tumor cells. Up to three (3) M-Trap devices will be surgically implanted via laparotomy in the right and left paracolic (pelvic) gutters and behind segment 6 of the liver within the peritoneal cavity of the patient at the time of surgical resection. Patients will receive standard platinum-based chemotherapy. If the cancer is diagnosed to have recurred, M-Trap devices with captured tumor cells will be removed via minimally invasive surgery (laparoscopy).

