## **5. SUBJECT SELECTION**

### **5.1. Inclusion Criteria (IC)**

Candidates for the study must meet ALL of the following inclusion criteria:

1. Is a female  $\geq 18$  years old.
2. Presents with a diagnosis of Stage IIIc or IV ovarian cancer.
3. Presents with high-grade serous carcinoma.
4. Has one of the following:
  - a. Stage IIIc disease and visible residual tumor  $\leq 1$  cm after primary tumor debulking surgery.
  - b. Stage IIIc or Stage IV disease and three or four cycles of neoadjuvant chemotherapy and complete resection after interval tumor debulking surgery.
  - c. Stage IIIc or Stage IV disease and three or four cycles of neoadjuvant chemotherapy and visible residual tumor  $\leq 1$  cm after interval tumor debulking surgery.
5. ECOG performance status of 0 or 1.
6. Is willing to comply with required follow-up study visits.

7. Is willing and able to provide written informed consent.

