## **5.2. Exclusion Criteria (EC)**

Candidates for this study will be excluded if ANY of the following conditions are present:

1. Has a life expectancy of <3 months.
2. Is pregnant, as confirmed through a blood test prior to any study procedure, planning on becoming pregnant during the study, or is lactating.
3. Will be receiving intraperitoneal chemotherapy.
4. Has undergone prior treatment with abdominal and/or pelvic radiotherapy.
5. Has significant active concurrent medical illnesses including, but not limited to, ongoing or active infection, symptomatic congestive heart failure, unstable angina pectoris, cardiac arrhythmia, or psychiatric illness/social situations that would limit compliance with study requirements.
6. Presence of central nervous system or cerebral metastases.
7. Recurrent ovarian cancer.
8. Complete resection with no residual tumor after primary tumor debulking surgery.
9. Suboptimal resection with > 1 cm residual tumor after primary or interval tumor debulking surgery.
10. Is simultaneously enrolled in another investigational study.
11. Has a history of cancer within 5 years other than in-situ uterine cervix cancer or non-melanoma skin cancer.
12. Has a known hypersensitivity to carboplatin or paclitaxel.
13. Is concurrently using other antineoplastic agents.

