##### **6.2.1. Debulking Procedure**

Debulking will be performed following the institution's standard protocols. A PCI must be documented pre- and post-debulking. In addition, all residual tumor will be documented on the Case Report Form. If possible, photographs should be taken, documenting the residual tumor.

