## APPENDIX 1 M-TRAP DEVICE EXPLANT PROCESSING PROTOCOL

Please follow this processing protocol after receiving a tissue specimen containing an M-Trap device.

1. Take high-resolution, clear photographs of the gross specimen. Please, establish the block identification key in a copy of the picture. (see step 4).
2. Measure and record tissue dimensions (length, width and thickness).
3. Identify the side that faced outward into the peritoneal cavity (marked with a surgical suture thread (X)) (Fig 1).

Fig 1:

[figure not shown]
4. Paint with ink (Indian ink) the side that was sutured against the abdominal wall and the surgical resection margins (Fig 2).

Fig 2:

5. Perform serial sectioning (10 sections of 0.3 cm) (the entire sample). For large samples (more than 3 cm width), include an additional cassette for each additional 1 cm of greatest dimension (Fig 3).

Fig 3:

[figure not shown]

6. Prepare blocks facing the side identified as A (Fig 4A, 4B).

Fig 4A:

Fig 4B:

7. Label the blocks with site number, patient code, M-Trap device code and the block number, from left to right: 1, 2, 3, 4...10.
  - a. Example: 03 01 A1, where 03 refers to the site number, 01 refers to the patient number, A refers to the M-Trap device code (\*see below) and 1 refers to the first block.
    - \* A: Right paracolic gutter
    - B: Left paracolic gutter
    - C: Liver segment (VI)
8. Fix the tissue in neutral buffered formalin for 16-24h at room temperature.
9. Process the tissue and embedded in paraffin following the department's pathology protocols.
10. Stain sections with Hematoxylin-Eosin.
11. Send the paraffin blocks, along with all photographs and the measurements of the tissue specimens, to the reference laboratory.

[name]/[name]  
Hospital Arnau de Vilanova, Anatomia Patològica  
[name]  
[name]

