2.4.3. Procedure (D0) Patients characteristics

Descriptive statistical data will be used to draw up a recapitulation of the intervention details at the time of the operation.

The following data will be presented on the ITT and the As-Treated populations:

- Physical exam: Weight (kg), BMI (kg/m²), Temperature (°C), Blood pressure (Systolic and Diastolic in mmHg), Heart rate (bpm), Specific abdominal examination performed (Yes/No), Presence of nodules or bumps if Yes (Yes/No) and How many nodules or bumps if Yes, Specific gynecologic examination performed (Yes/No), Presence of nodules or bumps in the cul-de-sac if Yes (Yes/No) and How many nodules or bumps in the cul-de-sac if Yes, Pre-operative serum albumin (g/dL) and Pre-operative hemoglobin (g/dL).
- Procedural Information: Type of debulking surgery, Debulking surgery duration (HH:MM), Pre-debulking PCI performed (Yes/No), PCI score if Yes, Detail of PCI scores (Region, Maximum lesion size (cm) and Lesion size score), Post-debulking PCI performed (Yes/No), PCI score if Yes, Detail of PCI scores (Region, Maximum lesion size (cm) and Lesion size score), Extensive upper abdominal surgical procedures (Diaphragm peritonectomy, Splenectomy, Full-thickness diaphragm resection, Partial hepatectomy, Distal pancreatectomy, Cholecystectomy), Other surgical procedures (Unilateral/bilateral salpingo-oophorectomy, Hysterectomy, Omentectomy, Large bowel resection, Pelvic lymph node dissection, Para-aortic lymph node dissection, Appendectomy, Thoracoscopy, Small bowel resection, Ileostomy, Colostomy, Inguinal lymph node dissection, Other), total number of extensive procedures, total number of other surgical procedures, total number of extended procedures (Patankar definition).Residual Tumor Characterization: Residual tumor observed after debulking (Yes/No), Can the patient be treated with M-Trap and the reasons if No, Device implant procedure duration (HH:MM), Suture used diameter (USP designation).
- Device: Successful implantation (Yes/No), The reason if No, Localization of implant.
- Post-Procedure Ultrasound: Abdominal ultrasound obtained (Yes/No), Reasons if No.
- Device deficiencies: Device malfunction occur during the procedure (Yes/No), If Yes Device deficiency description.

The analysis of the PCI and the residual tumor observed after debulking will be performed on PDS patients, IDS patients and overall.

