- Histopathologic evidence of tumor cell capture is “Yes” if Tumor cell infiltration for at least one device is >0 in a patient. Otherwise, Histopathological evidence of tumor cell capture is “No”.
- An AE will be considered as an SAE if “Serious Adverse event” = “Yes”.
- An AE will be considered “Unanticipated” if “Anticipated adverse event” = “No”.
- An AE will be considered as device related if “Relationship to device(s)” is “possible”, “probable” or “definite”.
- An AE will be considered as procedure related if “Relationship to procedure” is “possible”, “probable” or “definite”.
- At least one other medical history will be calculated as follows:

If at least one variable of other medical history is equal to “Yes” then “At least one other medical history” = “Yes”,

If no variable of other medical history is equal to “Yes” then:

- If all variables of other medical history are equal to “No” then “At least one other medical history” = “No”,
- If at least one variable of other medical history is equal to “Missing” then “At least one other medical history” = “Missing”,

If all variables of other medical history are equal to “Missing” then “At least one other medical history” = “Missing”.

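### Any tumour cells in any one device count as capture, so ingrowth from residual tumour beside a device is not separated from capture of disseminated cells

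*SAP*

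**What the plan says.** **Purpose.** Protocol section 2 states: "M-Trap is intended to be implanted into the peritoneal cavity during the tumor debulking procedure to capture disseminating tumor cells". The primary performance objective (Protocol section 4, SAP 1.1) is to confirm performance from histology of the explanted devices.

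**Capture rule.** SAP 2.5 sets capture to Yes if "Tumor cell infiltration for at least one device is >0 in a patient", and to No otherwise. The core-laboratory item behind it is an infiltration percentage (SAP 2.4.7). Protocol 10.3 also needs only one positive device and takes recurrent patients as the denominator. SAP 2.4.5 analyses the As-Treated population, by device location and in recurrence sub-populations.

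**Population.** Inclusion criterion 4a requires "Stage IIIc disease and visible residual tumor" of at most 1 cm after primary debulking. Exclusion criterion 8 removes patients with "Complete resection with no residual tumor after primary tumor debulking surgery". Interval-debulking patients may have either complete resection or residual tumour up to 1 cm.

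**Placement.** Protocol 6.2.2 names three fixed sites and has each mesh sutured flat against the wall. It sets no condition on tumour at the site. Protocol section 2 describes a porous matrix that tissue can grow into. Under Protocol 6.2.3 a device may stay in place until the 18-month time point.

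**Data already collected.** Protocol 6.2.1 says that "all residual tumor will be documented on the Case Report Form" and requires a post-debulking PCI. SAP 2.4.3 records that PCI by region, with lesion size and score, and the location of each implant. Appendix 1, step 4, adds: "Paint with ink (Indian ink) the side that was sutured against the abdominal wall and the surgical resection margins".

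**Planned tables.** SAP Tables 58 and 59 split capture by device location and recurrence status only.

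**The concern.** The device is meant to catch cells that travel through the peritoneal cavity. The rule records only whether tumour cells are present in the mesh. In a patient with visible tumour left behind, cells can also reach the mesh by direct growth from tumour under or next to it. The rule gives the same answer in both cases.

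The plan itself foresees local growth at the device. Protocol 7.1.1 lists cancer progression through the abdominal wall at the device suture sites as a device-specific adverse event. Protocol 4.1.1 counts it in the primary safety endpoint when it leads to removal within 6 months. A device removed for that reason, with infiltration above zero, would be a safety failure and a capture success at once.

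At stake is what the trial can say about mechanism. In a single-arm study supporting CE-marking, a high capture percentage will be read as capture of disseminated cells. Without a split by residual tumour, the reader cannot tell how much of it depends on devices sited close to tumour that was never removed.

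**Working it through.** **1. The plan's own figure.** There is no target rate, threshold or sample size for capture. The only sample size is for safety: n=20, 65% against 90%, one-sided 5%. The exact binomial rule is success at 17 or more of 20, with alpha 0.044 and power 0.867, so the stated power above 85% reproduces. It has no bearing on capture.

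**2. The rule applied to two devices.**

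| | Device A: cells arrived through the cavity | Device B: ingrowth from adjacent residual tumour |
|---|---|---|
| Infiltration | above 0 | above 0 |
| SAP 2.5 result | Yes | Yes |
| Row in Tables 58 and 59 | its location, recurrence status | its location, recurrence status |

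**3. Whether another planned output separates A from B.**
- Immunohistochemistry (Protocol 6.6.7) characterises the tumour cells and the immune response. It is given no role in establishing the cells' route.
- The focalization score (Protocol 6.2.3) grades the share of recurrent disease held in the devices. An overgrown device also scores well.
- Washings, ascites cytology and biopsies (Protocol 6.6.8) describe disease outside the device.
- Listings 11, 13, 14, 22 and 28 (SAP 4.2) hold PCI detail, residual tumour, implant, capture and pathology data by patient. They allow a comparison by hand, but none is prespecified.

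**4. Sensitivity of the estimate to a few patients.** Protocol 1.5 gives about 40% to 50% progression at 12 months. Applied to 20 evaluable patients, this is 0.40 × 20 = 8 to 0.50 × 20 = 10 recurrent patients (illustrative; follow-up runs to 18 months). The exact one-sided 90% lower bound L solves P(X ≥ x | n, L) = 0.10, that is, the 0.10 quantile of Beta(x, n − x + 1). When x = n, L = 0.10^(1/n).

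| Positive / recurrent | Estimate | Lower bound |
|---|---|---|
| 10/10 | 100% | 79.4% |
| 9/10 | 90% | 66.3% |
| 8/10 | 80% | 55.0% |
| 7/10 | 70% | 44.8% |
| 8/8 | 100% | 75.0% |
| 7/8 | 87.5% | 59.4% |
| 6/8 | 75% | 46.2% |

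Each reclassified patient moves the estimate by 10 to 12.5 points and, in the steps shown, the bound by about 10 to 16 points. The denominator matters too. If two of ten patients are recoded as not captured, the result is 8/10 (bound 55.0%). If they leave the analysis because they have no usable device, it is 8/8 (bound 75.0%).

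**5. Effect of needing only one positive device.** Let q be an assumed chance that a given device is positive through ingrowth alone, with three independent devices. The chance of a patient-level Yes from ingrowth is 1 − (1 − q)³: 5.9% for q = 2%, 14.3% for 5%, 27.1% for 10% and 48.8% for 20%. The documents give no value for q, so this is a range and not an estimate.

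**The case against.** The strongest reply has four parts.

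**No test can be falsely passed.** Capture is reported with a one-sided 90% interval and no hypothesis. This stands. A reader might infer that the trial would wrongly prove its mechanism; the documents do not support that, because they set no bar to clear.

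**Not every patient is affected.** Interval-debulking patients with complete resection have no visible residual tumour, and their share of the trial is not fixed. This also stands. The point applies to primary-debulking patients and to interval patients with residual tumour.

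**The size cannot be derived.** A reader might try to obtain it from geometry. With k of 13 PCI regions holding residual tumour at random and devices in three distinct regions, the chance of at least one shared region is 1 − C(10,k)/C(13,k): 23.1%, 42.3% and 58.0% for k = 1, 2 and 3. The arithmetic is right, but it does not measure bias. Sharing a region is not contact with a 15 × 50 mm mesh. The values of k, the random placement and the three distinct regions are all assumptions, and Protocol 6.6.6 neither names the regions nor links them to device sites.

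**PCI score does not identify mechanism.** A score of 0 means only that no tumour was seen, so microscopic tumour may remain. A device in a region scoring 1 or more may still hold disseminated cells. A reader might conclude that the capture claim should rest on score-0 devices alone. That goes too far: it could misclassify in both directions and discard informative devices.

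What remains is that the listings allow only a comparison by hand. With so few patients, a split chosen after the explant results are known would carry little weight.

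**Conclusion.** The concern holds in a limited form. The capture rule does not consider where the cells came from, the eligibility criteria guarantee visible residual tumour in one group and allow it in the other, and no planned table relates device positivity to residual tumour at the device site. The size and frequency of any effect are unknown. The bounds above show only that, with roughly 8 to 10 recurrent patients, one or two ambiguous positives matter to the reported result. That rests on applying the 12-month progression range to 20 patients and on an assumed starting result in which every recurrent patient is positive.

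This is an interpretive gap that should be closed before explant results are known. It does not invalidate the endpoint, and the all-device percentage remains a proper summary of tumour cells found in the devices.

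**What to change.** In SAP 2.4.5, SAP 2.5 and Tables 58 and 59:

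1. Map each of the three device sites to its PCI region.
2. Tabulate device-level capture by the post-debulking lesion size score of that region, 0 versus 1 or more, with a separate row where the score is missing.
3. Add a prespecified patient-level sensitivity analysis that counts only devices in score-0 regions, with the same exact one-sided 90% interval. State its denominator and how many patients have no score-0 device. Show it also for patients with and without visible residual tumour after debulking.
4. Keep the all-device result as the primary estimate and print the sensitivity result beside it. If the two differ, qualify any statement about capture of disseminated cells.
5. State that a score of 0 does not exclude microscopic residual tumour.

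**Cost.** A SAP edit, a short site-to-region map and a few table rows, all from data already planned. The downsides are smaller numbers in the score-0 version and a possibly less favourable percentage. Recording which face of the device the tumour involves would need a new core-laboratory item: Appendix 1 has the faces marked, but SAP 2.4.7 lists no such variable. The changes above do not depend on it.

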2.1.2. Handling Missing Data

In order to provide unbiased and informative findings, no replacement of missing values is planned for any parameters.

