2.1.5. Interim Analysis

An interim analysis will be performed after all patients reach the 6-month time point to support the CE-marking application.

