2.4.5. Primary Analysis

Primary analysis of safety will be performed on the ITT population and the As-Treated populations.

The primary safety endpoint is freedom from device and procedure-related major adverse events through 6-months post-implantation, including shock, cardiac arrest, myocardial infarction, pulmonary embolism, prolonged intubation, unplanned reintubation, or adverse events leading to removal of the device, including infection, seroma formation, mesh migration, bowel obstruction, adhesions, and local cancer progression through the abdominal wall at M-Trap suture sites.

The primary safety endpoint will be analyzed using a unilateral one sample test for binomial proportion at the 5% level. In addition, the exact bilateral 95% confidence interval will also be given. The statistical test for the primary safety endpoint is given by:

- H0: M-Trap freedom MAE incidence \leq 90% - Non-inferiority margin (25%)
- Versus
- HA: M-Trap freedom MAE incidence $>$ 90% - Non-inferiority margin (25%)

A modified primary analysis will also be performed that uses a freedom from MAE incidence rate that is adjusted for the surgical complexity of the study population, as compared to the Patankar study population, which is the basis of the statistical rationale for this study (repeated in the table below). The total number of extended procedures will be split in four classes: 0, 1, 2, 3 and more.

Procedures	0	1	2	3 or more	AVG
Total patients	1352	1214	254	50	2870
Severe complications, n	51	92	44	9	196
Severe complications, %	3.8%	7.6%	17.3%	18.0%	6.8%

A further modified primary analysis will also be performed that only includes procedure-related events through 30 days, as this is the comparable population to the Patankar study population, which is the basis of the statistical rationale for this study.

Primary analysis of performance will be performed on the As-Treated population and by device location. This analysis will be also performed using these 3 following sub-populations: (1) platinum resistant, recurrent patients; (2) platinum sensitive, recurrent patients; (3) non-recurrent patients (see definition in part 2.5).

The primary performance endpoint is histopathologic evidence of tumor cell capture (see 2.5). Histopathology will be performed after device explant.

The primary performance endpoint will be assessed with exact one-sided 90% confidence intervals.

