2.4.7. Device Removal

Descriptive statistical data will be used to draw up a recapitulation of the device removal details at the time of the removal operation.

The following data will be presented on the As-Treated population on patients number:

- Duration until device removal (days), Reason for removal, All devices removed (Yes/No), The number of devices removed if No. Duration until device removal (days) if the reason for removal is recurrence.
- The time to recurrence will be described using a Kaplan Meier curve. Patients lost to follow-up before the removal will be censored at the date of last follow-up. Patients who have removal for another reason than recurrence before the 18 months will be censored at the date of the removal.
- Disease Focalization: Disease focalization score, Modalities used for the assessment of disease focalization, If a peritoneal wash performed, were malignant cells present (Yes/No)
Disease Focalization will be also analyzed using the 3 sub-populations defined below ((1), (2), (3)), and using the populations (1) and (2) combined and overall.
- Adverse Event: New adverse event(s) occur during removal procedure (Yes/No)
- Cytology (Done with final device removal): Where ascites present (Yes/No), Were malignant cells present in the ascites (Yes/No), Was a peritoneal wash performed (Yes/No), From which area was the wash obtained if "Yes", Were malignant cells present in the peritoneal wash.

	STATISTICAL ANALYSIS PLAN	MTRAP_SAP_v2.0_FINAL redacted.docx
		MTRAP Page 14/15

- Biopsies (Done with final device removal): Biopsy location, Biopsy taken (Yes/No), Is visible tumor present (Yes/No), Is microscopic disease present (Yes/No)

If Biopsy location is Adhesive bands, abnormally scarred areas or Retroperitoneum the further details given will be described by the mean of listing.

The following data will be presented on the As-Treated population on devices number:

- Location of Device, Attachment of the device to the surrounding tissues
- Assessment of device removal: Ease of locating M-Trap device, Did the M-Trap device remain securely fixed in its original location, Ease of removing M-Trap device, Endobag used, Trocar size (mm)
- Core Lab: Device(s) sent to the core laboratory (Yes/No), the Reasons and the Location if No

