2.5. Derived Criteria Calculation

If at least one of the items needed to calculate a derived criterion is missing then the corresponding derived criterion will be considered as missing.

- Derived criterion “ITT population” will be defined as follows:

If “Signed Informed Consent” = “Yes” and the date of signature of the consent form is filled and all inclusion/exclusion criteria are compliant and “Can the patient be treated with M-Trap” = “Yes” then “ITT population” = “YES”, else “ITT population” = “NO”.

- Derived criterion “As-Treated population” will be defined as follows:

If the date of signature of the consent form is filled and are compliant with all inclusion/exclusion criteria and “Can the patient be treated with M-Trap” = “Yes” and at least one device successfully implanted then “As-Treated population” = “YES”, else “As-Treated population” = “NO”.

- Derived criterion “Age at Enrollment” will be calculated as follows:

“Age at Enrollment” = “Date of signature of Informed Consent” – “Birth date” in years

- Derived criterion “Duration of patients Follow-up” will be calculated as follows:

“Duration of patients Follow-up” = “Last patient follow-up date” – “Procedure patient date”

If patient procedure date is missing Baseline/Screening date will be used (for ITT population)

- Derived criterion “Duration debulking surgery” will be calculated as follows:

“Duration debulking surgery” = “end time of debulking surgery” – “start time of debulking surgery”

- Derived criterion “Duration of implantation” will be calculated as follows:

“Duration of implantation” = “end time of implantation” – “start time of implantation”

- Derived criterion “Total number of procedures” will be equal to the number of checked boxes for “Extensive upper abdominal” and “Other procedures”.

- Derived criterion “Total number of extensive procedures” will be equal to the number of checked boxes for “Extensive upper abdominal”.

CRO will send to MTrap an Excel file with the list of all other surgical procedures to count their number.

- Derived criterion “Number of extended procedures (Patankar definition)” will be calculated as follows:

All patients start with a score of 1, since all patients had cytoreduction surgery.

Add 1 to the score if Pelvic or Para-aortic or Inguinal lymph node dissection are ticked or if any other procedure includes lymph node dissection (lymphadenectomy).

STATISTICAL ANALYSIS PLAN

Add 1 to the score if Small bowel resection is ticked.

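### SAP 2.5 gives two conflicting rules for tumor cell capture when a device is not explanted or not read, with no order of precedence; one of them counts never-examined As-Treated patients as non-captures

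*SAP*

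**What the plan says.** **The endpoint rule.** SAP 2.5 scores a patient Yes for histopathologic evidence of capture if "Tumor cell infiltration for at least one device is >0 in a patient". It continues: "Otherwise, Histopathological evidence of tumor cell capture is “No". It sets no condition that any device was explanted or read.

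**The general rule.** The same section opens with: "If at least one of the items needed to calculate a derived criterion is missing then the corresponding derived criterion will be considered as missing". No order of precedence between the two is given.

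**Missing data.** SAP 2.1.2 says "no replacement of missing values is planned for any parameters", and SAP 2.1.3 bases percentages on non-missing observations.

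**The analysis set.** SAP 2.4.5 states: "Primary analysis of performance will be performed on the As-Treated population and by device location". SAP 2.3.1 requires only one implanted device for membership. Protocol 10.3 instead defines the endpoint as a percentage of recurrent patients.

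**Unread devices are foreseen.** SAP 2.4.7 records whether all devices were removed, and also "Core Lab: Device(s) sent to the core laboratory (Yes/No), the Reasons and the Location if No". Protocol 6.2.2 implants three devices per patient.

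**The interim.** SAP 2.1.5 states: "An interim analysis will be performed after all patients reach the 6-month time point to support the CE-marking application". It does not list the endpoints to be analysed.

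**The concern.** Histology exists only for a device that has been taken out and read. A patient who dies or is lost with devices in place, or whose explants are not read, has no information on capture. The endpoint rule nevertheless records her as a non-capture, so the percentage mixes devices examined and found negative with devices never examined.

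The general rule treats the same patient differently. Taken literally, it also causes the opposite error, because a patient with one proven capture and one unread device leaves the analysis. Two programmers could each follow SAP 2.5 and report different primary performance results.

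The endpoint has no target, threshold or power calculation. The estimate and its exact one-sided 90% limit are the whole performance result, and a stated study objective is to support CE-marking.

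**Working it through.** **1. The two rules side by side**

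| What is on record | Endpoint rule | General rule, read literally |
|---|---|---|
| No device read | No | Missing |
| One positive, at least one unread | Yes | Missing |
| All read devices negative, at least one unread | No | Missing |
| All implanted devices read, all negative | No | No |

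The rules disagree in the first three rows.

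For comparison, the same list in SAP 2.5 gives the variable for other medical history a full scheme: any Yes is Yes, all No is No, and no Yes with something missing is missing. The capture endpoint has no such scheme. Tables 58 and 59 use the Type 2 layout, which has no Missing row, unlike Type 5.

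**2. Effect of patients with nothing read**

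The documents give no expected capture rate and no performance sample size, so there is no plan figure to reproduce. The following data are assumed. N = 22 is the planned maximum treated. Two unread is the gap between 22 treated and 20 evaluable, and 1 and 4 bracket it. For x captures among n, the exact one-sided 90% lower limit is the 0.10 quantile of Beta(x, n − x + 1).

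| Assumed case | Unread = No | Unread = missing |
|---|---|---|
| 1 unread, all read positive | 21/22 = 95.5% (83.4%) | 21/21 = 100% (89.6%) |
| 2 unread, all read positive | 20/22 = 90.9% (77.6%) | 20/20 = 100% (89.1%) |
| 4 unread, all read positive | 18/22 = 81.8% (66.9%) | 18/18 = 100% (88.0%) |
| 2 unread, 16 captures | 16/22 = 72.7% (57.0%) | 16/20 = 80.0% (63.9%) |

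**3. Both rules on one data set**

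Assume 22 patients: 14 positive with all devices read, 4 positive with at least one device unread, 2 fully read and negative, 2 with nothing read.

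- Endpoint rule: (14 + 4)/22 = 18/22 = 81.8%, limit 66.9%.
- General rule, literal: 14/(14 + 2) = 14/16 = 87.5%, limit 70.0%.
- Any read positive is Yes, nothing read is missing: 18/(18 + 2) = 18/20 = 90.0%, limit 75.5%.

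**4. The recurrent-patient percentage**

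SAP 2.5 defines recurrence by the reason for device removal. A never-explanted patient has no such reason and falls among the non-recurrent, so she does not enter the percentage in protocol 10.3. Unread explants still matter there. In an assumed 10 recurrent patients with 2 unread and the rest positive, 8/8 (75.0%) becomes 8/10 = 80.0% (55.0%).

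**5. The 6-month interim, if capture is reported there**

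Protocol 6.2.3 leaves devices in until an adverse event, progression or month 18. Assume uniform enrollment over the 9 months in the synopsis, exponential progression at the 40-50% by 12 months in protocol 1.5, and removal at once on progression. When the last patient reaches month 6, follow-up runs from 6 to 15 months. The explanted fraction is 1 − (e^(−6λ) − e^(−15λ))/(9λ), with λ = −ln(1 − p)/12.

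- p = 0.40: 0.357, or 7.8 of 22.
- p = 0.45: 0.402, or 8.9 of 22.
- p = 0.50: 0.449, or 9.9 of 22.

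With 9 explanted and every one positive, 9/9 = 100% (77.4%) would be reported as 9/22 = 40.9% (26.4%).

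**6. Partly read, all-negative patients**

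A repair that keeps partly read positives but drops partly read negatives has a bias of its own. Assume three independent devices, each with a 30% chance of capture and a 20% chance of being unread.

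- True patient rate: 1 − 0.7³ = 65.7%.
- At least one device read and positive: 1 − (1 − 0.3 × 0.8)³ = 1 − 0.76³ = 56.1%. This is also the rate under the endpoint rule.
- All devices read and negative: (0.8 × 0.7)³ = 17.6%.
- Nothing read: 0.2³ = 0.8%.
- Partly read negatives dropped: 56.1/(56.1 + 17.6) = 76.2% (unrounded inputs).
- Partly read negatives counted as No: 56.1/(100 − 0.8) = 56.6%.

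The two treatments fall on either side of the true rate, so neither should stand alone.

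**The case against.** The strongest reply is that the general rule heads SAP 2.5 and governs every criterion below it. A patient with nothing read is then missing, which fits the policies in SAP 2.1.2 and 2.1.3. That rule also concerns only items needed for the calculation; once one device is positive, the others are arguably not needed. Read this way, most of the conflict disappears. The reading is sensible, but the SAP does not state it for this endpoint, although it spells out the equivalent scheme for medical history. Partly read negatives would also remain unclear.

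Several further points stand and limit the concern:

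- Protocol 6.7.2 plans device removal before withdrawal, so unexplanted patients would come mainly from death or loss to follow-up.
- The default No is conservative, and no formal test depends on it.
- Table 91 and Listings 22, 26 and 28 should let a careful reader separate unread from negative.
- The interim model ignores the pause between phases, removal only after chemotherapy, and the need to meet both progression criteria. These would lower the explanted count. The SAP also does not say that capture is analysed at that point.

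A reader might infer three stronger things. The first is that the SAP definitely counts unread patients as failures; this is only one of two readings the text allows. The second is that a single patient could be No, missing or Yes. No pattern in the table above gives all three. The third is that limiting the analysis to recurrent patients leaves the problem whole; the recurrence definition keeps never-explanted patients out of that percentage.

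**Conclusion.** The concern holds as a conflict between two rules. SAP 2.5 does not define the primary performance endpoint uniquely when devices are unexplanted or unread, which the SAP itself foresees.

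Under the endpoint rule, the As-Treated and non-recurrent capture rates are biased downward. With 2 of 22 patients unread, the point estimate falls by 7 to 9 percentage points and the lower limit by 7 to 12. The general rule, read literally, removes proven captures and can move the estimate either way. The recurrent-patient percentage is affected only through partial removal or unread explants. The distortion would be larger at the 6-month interim if capture is reported then, because many devices would still be implanted.

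The number unread and the capture rates are assumptions. Treating the unread as missing also assumes that their capture resembles that of read patients, so a worst-case line is needed. The safety endpoint and its sample size are not affected.

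**What to change.** Replace the rule in SAP 2.5 and state that it overrides the general missing-item rule for this endpoint:

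- **Yes:** any read device has infiltration above zero, whatever the status of the others.
- **No:** every implanted device was read and has infiltration of zero.
- **Missing:** no device was read. The patient leaves the denominator, in line with SAP 2.1.2 and 2.1.3.
- **All read devices negative, at least one unread:** report the rate and its limit both ways, once counted as No and once as missing.

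In Tables 58 and 59, add a Missing row and the numbers of patients and devices implanted, explanted and read. Report any interim capture result among patients with read devices only. Keep unread = No as a worst-case sensitivity line.

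The work is a paragraph of SAP text, one programming rule and a table change. The price is a smaller denominator, a wider interval and, where devices are partly read, a range instead of one figure.
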